Post-intensive care syndrome (PICS) is a common consequence of an intensive care unit (ICU) stay and can last up to 5 years.[1–3] The family members are often affected, reporting diminished quality of life and mental health related quality of life.[4] About 80% of family members become informal carers and 33% of families

see a significant reduction of income the first 6 months after discharge.[5] The extent to which these problems will be modified by the pandemic and coronavirus disease 2019 (COVID-19) remains unknown.

If under normal circumstances, an ICU stay has detrimental effects, the pandemic added two extra factors. Firstly, a rapid and exponential increase in acute care bed capacity might have affected the quality of care delivered by spreading too thin highly skilled healthcare staff. Secondly, COVID-19 involves a new disease with great uncertainties regarding treatment, prognosis and long-term effects. Early reports suggest that 64% of patients who were discharged from ICU after severe COVID-19 have at least one symptom of PICS at 6 months after discharge[6] and 32% had anxiety or depression symptoms,[7] which suggests these patients will have similar impairments to what has been reported for other ICU survivors previously.[8,9] Additionally, infection control protocols meant that healthcare staff had to wear personal protective equipment and family visiting was restricted.[10] These factors add another layer of potential negative effects due to challenges in communication with patients and their family members. Therefore, we hypothesize that the prevalence and severity of mental, physical, and cognitive impairments will be higher in patients treated in periods of higher bed occupancy and those who had severe COVID-19. In the case of family members, we expect that the experience of having a next of kin in the ICU during pandemic would be stressful and traumatic, but those with social support will cope better. In the case of staff members, their experiences will vary greatly depending on their profession and workplace, but we expect places with a more open/ less hierarchical structure to have coped better with the increase in demand.

The primary objective of this study is to compare the trajectory of mental, physical and cognitive impairments at ICU discharge, 3 and 6 months of mechanically ventilated adult patients who survived an ICU stay due to severe COVID-19 or other causes, during the pandemic. Secondary objectives are:

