- To compare the disability, quality of life and survival rate at ICU discharge, 3 and 6 months of patients who were admitted to ICU due to severe COVID-19 or other causes during high and low bed occupancy in the pandemic;
- To describe the sedentary behaviour and physical activity levels in a sample of ICU survivors during the COVID-19 pandemic using a one-week actigraphy protocol;
- To explore the psychological and emotional experiences reported by family members/next of kin of patients admitted to the ICU during the COVID-19 pandemic;
- To explore the emotional, intellectual, physical and administrative challenges faced by the participating ICU staff during the COVID-19 pandemic;
- To evaluate the feasibility of the follow-up from ICU discharge to 3 and 6 months during the pandemic.

METHODS

Study design and setting

The “Impact on Mental, Physical, And, Cognitive functioning of Critical care Time due to COVID-19” (IMPACCT-COVID19) is a prospective, multicentre, cohort study in seven Chilean academic medical-surgical ICUs. This study also involves a

qualitative component including semi-structured interviews with family members/next of kin of ICU survivors and with ICU staff from the participating centres. Participating sites are four public and three private hospitals comprising a pooled bed capacity of about 200 ICU beds for both COVID-19 patients and patients admitted for other causes. The IMPACCT-COVID19 study started in October 2020. Data collection is planned until November 2021 to achieve completion of the study in February 2022.

Study population and eligibility criteria

Adult patients (≥ 18 years old) who are mechanically ventilated for at least 48 hours in one of the participating ICUs and do not meet any of the exclusion criteria (**Table 1**) will be invited to participate.

Table 1. Exclusion and stopping follow-up criteria

Exclusion criteria	Rationale
Unable to walk independently 2 weeks prior to ICU admission (with or without a gait aid)	Potential confounding factor
S5q < 5 or CAM-ICU positive within 72 hours after ICU discharge	Unable to evaluate
Patient who do not understand or speak Spanish	Unable to evaluate
Patient unable to communicate verbally	Incomplete assessment data
Burn or severe trauma as admission diagnosis	Incomplete assessment data
Any neurological disorder (i.e. spinal cord injury, stroke and brain tumours) as admission diagnosis	Potential confounding factor

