The primary outcome measure is disability assessed at 6 months after ICU discharge using the World Health Organization Disability Assessment Schedule 2.0 (WHODAS 2.0) which is recommended for critical illness survivors.[8] The WHODAS 2.0 is a self-reported disability questionnaire based on the International Classification of Functioning, Disability, and Health (ICF). It includes 36 questions, organised under six domains (cognition, mobility, self-care, getting along, life activities and participation). Each question must be answered based on the perceived difficulty for performing activities using a 5-point scale (none, mild, moderate, severe and extreme).[15] We will use the Spanish version freely

available at <https://apps.who.int/iris/handle/10665/170500>.[16] The estimated response time ranges from 5 to 10 minutes when evaluated in-person at ICU discharge and 10 to 20 minutes when evaluated by telephone at 3 and 6 months after ICU discharge.

Secondary outcomes measures

Clinical Frailty Scale

The Clinical Frailty Scale (CFS) is a clinical judgment based tool developed for the Canadian Study of Health and Aging to evaluate the degree of frailty in elderly patients.[17] Currently, it is also used for critically ill patients.[18] The CFS evaluates specific domains including physical functioning, activities of daily living (ADL), instrumental ADL, assistance for personal care, comorbidities, and cognition to generate a frailty score using a 9-point scale ranging from 1 (very fit) to 9 (terminally ill). A score greater than 4 is considered fragile.[17] We will use the Spanish version and recommended training material by the developers at the Dalhousie University.[17,19] The estimated scoring time ranges from 1 to 5 minutes evaluated in-person at ICU discharge considering the status 2 weeks before the onset of symptoms.

Medical Research Council Sum Score (MRC-SS)

Limb muscle strength will be assessed using the MRC-SS, which consists in a standardised examination of six muscle groups bilaterally (i.e. shoulder abduction, elbow flexion, wrist extension, hip flexion, knee extension and dorsiflexion).[20] All muscle groups are scored using a 6-point scale between 0 and 5 (0 = no visible /

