The trajectory for each outcome measure will be estimated using longitudinal multilevel regression with robust standard errors to account for data coming from

seven treatment centres. If data have a normal distribution, a linear regression model will be chosen. In the case of right skewed data, a Poisson regression will be used. For HADS, IES-R and WHODAS 2.0, data will be analysed as total scores and categories given by each questionnaire.

Survival will be analysed using Kaplan-Meier curves. If the assumption of proportional hazards is met, survival will be compared between patients admitted due to COVID-19 vs. other causes using Cox regression. All analyses will be performed in Stata 16.0 SE.

Qualitative analysis

Data from the interviews with family members and critical care staff will be analysed using framework analysis.[43] Transcription will be aided by the software Scrintal and analysis by Nvivo 12.0. Two coders will listen and read in-full all interviews before meeting to explore potential common topics that were discussed during the interviews. These topics will form the initial coding framework. Through an iterative process these codes will be refined into overarching themes capturing differences and similarities across subgroups. A more advanced coding framework will be reviewed with members of the research team until agreement regarding the final framework is reached.

Themes will be used to explain the experience of family members during the pandemic and, potentially, identify areas where improvements could be made in the future. In the case of critical care staff, the aim is to explore to what extent the approach to the pandemic of each centre influenced the experience of the different clinical groups, and what can be learned for future outbreaks.

Findings will be shared with our participants and with other family members/ critical care staff that did not participate in the interviews to ensure our interpretation reflects their experiences.

Patient and public involvement

Patients or the public were not involved in the design, conduct, reporting, or dissemination plans of this study.

ETHICS AND DISSEMINATION

Ethical considerations

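### The primary objective (impairment trajectories, COVID-19 against other causes) matches neither the declared primary outcome (WHODAS 2.0 disability at 6 months) nor the contrast used for the sample size

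*Combined protocol and SAP*

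**What the plan says.** The Introduction gives the primary objective as to "compare the trajectory of mental, physical and cognitive impairments at ICU discharge, 3 and 6 months" in ventilated adults "who survived an ICU stay due to severe COVID-19 or other causes, during the pandemic". Disability is not mentioned there.

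The list that opens with "Secondary objectives are" has as its first item: "To compare the disability, quality of life and survival rate at ICU discharge, 3 and 6 months". That item also brings in high and low bed occupancy.

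Under Measurement Outcomes the plan declares: "The primary outcome measure is disability assessed at 6 months after ICU discharge", measured with WHODAS 2.0. MRC-SS, FSS-ICU, MoCA-blind, HADS and IES-R all follow under the heading for secondary outcome measures.

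The Sample size calculation section lists four scenarios in Table 3, three on WHODAS 2.0 and one on HADS. It then calls one of them the most plausible: 40% with some degree of disability in a low-demand period against 64% in high-demand periods.

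The Quantitative analysis section plans a longitudinal multilevel regression for each outcome. For HADS, IES-R and WHODAS 2.0, "data will be analysed as total scores and categories given by each questionnaire".

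**The concern.** A primary objective, its outcome, its sample size and its main analysis should describe one question. Here the named primary outcome serves a secondary objective, and the instruments that serve the primary objective are all labelled secondary. The contrast differs as well: COVID-19 status in the primary objective, demand period in the sample size.

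At stake is what the study report may call its main answer. Suppose WHODAS 2.0 at 6 months shows little difference by demand period, while an IES-R or MoCA-blind trajectory differs by COVID-19 status. The second result could be presented, with support from the text, as answering the primary objective, although the study was not sized for that outcome or that contrast.

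**Working it through.** **1. The sections side by side**

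| Section | Construct | Time | Contrast |
|---|---|---|---|
| Primary objective (Introduction) | Mental, physical and cognitive impairments | Trajectory over ICU discharge, 3 and 6 months | COVID-19 against other causes |
| First secondary objective (Introduction) | Disability, quality of life, survival | ICU discharge, 3 and 6 months | COVID-19 or other causes, under high and low occupancy |
| Primary outcome (Measurement Outcomes) | Disability, WHODAS 2.0 | 6 months | None named |
| Chosen scenario (Sample size calculation) | WHODAS 2.0, some degree of disability | Patient number set for 6 months | High- against low-demand periods |
| Quantitative analysis | Every outcome alike; WHODAS as score and as categories | Trajectory | Named only for survival (COVID-19 against other causes) |

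The primary-objective row agrees with neither the primary-outcome row nor the sample-size row. Occupancy or demand is not mentioned in the Quantitative analysis section, and the documents do not define which periods count as high or low demand. The columns of Table 3 carry yet another label, non-pandemic against pandemic, although all patients are recruited during the pandemic.

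**2. Can the primary objective be served by its own instruments?** Table 2 schedules HADS, IES-R and MoCA-blind at all three visits. MRC-SS and FSS-ICU are done only at ICU discharge, so the dedicated physical measures cannot give a trajectory.

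**3. The plan's own figures.** Retention: 550 × 0.75 = 412.5 (stated 413), and 412.5 × 0.70 = 288.75 (stated 289). This reproduces, so the recruitment target is tied to the WHODAS scenario's requirement of 288.

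The 288 itself does not follow from the stated inputs with equal groups. With p1 = 0.40, p2 = 0.64, mean 0.52, two-sided alpha 0.05 and power 0.8:

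n per group = [1.96·√(2 × 0.52 × 0.48) + 0.8416·√(0.40 × 0.60 + 0.64 × 0.36)]² / 0.24² = (1.385 + 0.577)² / 0.0576 ≈ 66.8, so 67 per group and 134 in total (150 with continuity correction).

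The allocation ratio and any inflation for centres are not stated, so this does not show 288 to be wrong. It is a separate matter, and the present point does not rest on it.

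**4. What a change of contrast does to power.** The documents give no split of patients by COVID-19 status or by demand period. As an assumption, take 289 patients, the same 40% and 64%, and no allowance for centre clustering:

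power = Φ{(0.24 − 1.96·SE0)/SE1}, with SE0 = √[p̄(1 − p̄)(1/n1 + 1/n2)] and SE1 = √[p1(1 − p1)/n1 + p2(1 − p2)/n2].

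- Higher-risk group 50% of patients: 98.6%
- 30%: 96.8%
- 20%: 91.4%
- 10%: SE0 = 0.0969, SE1 = 0.0943, (0.24 − 0.1899)/0.0943 = 0.53, power 70.2%

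Power therefore depends on a split that the plan does not state. The rates, too, are given for demand periods and not for COVID-19 status.

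**The case against.** The plan does name one instrument and one time point as primary and sizes the study on that instrument. WHODAS 2.0 is described as including cognition and mobility domains and is repeated at all three visits, so it overlaps with the constructs of the primary objective. The study is an observational cohort to be reported under STROBE, and the documents claim no confirmatory standing. These points stand and limit the concern. They do not remove it: no section says that WHODAS 2.0 represents the three impairments, Table 2 lists it under a heading of its own, and one time point is not a trajectory.

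Several stronger readings are tempting but not supported:

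- A reader might infer that HADS, IES-R or MoCA-blind could equally be reported as the primary outcome. The explicit designation rules that out; what remains open is which result answers the primary objective.
- A reader might attach a false-positive rate: 1 − 0.95⁴ = 18.5% for four scores, or 1 − 0.95¹² = 46% for four scores at three visits. Both assume independent tests. The second also assumes separate tests at each visit, whereas the plan specifies a longitudinal model. Neither figure should be used.
- A reader might infer that three WHODAS definitions compete. Table 3 presents scenarios, and the text below it selects one. The remaining ambiguity is total score or categories.
- A reader might infer that the study is underpowered for COVID-19 status. The documents give neither the split nor the rates needed to show that.

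**Conclusion.** The mismatch is real, and no section reconciles it. The primary objective differs from the declared primary outcome in construct and timing, and from the chosen sample-size scenario in contrast; the analysis section does not settle which governs. Its size is qualitative: no error rate or loss of power can be derived from the documents. The conclusion assumes only that the objectives and the outcome designation mean what they say, and that WHODAS 2.0 was not meant as an unstated summary of the three impairments. Because one primary outcome and time point are already named, and alignment needs rewording only, this is a should-fix.

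**What to change.** - Reword the primary objective to compare WHODAS 2.0 disability at 6 months between patients discharged in high- and low-demand periods, the contrast already used for the sample size, and define those periods.
- If COVID-19 status is kept as the primary contrast instead, restate the sample-size basis for it, with expected rates and group split.
- Name some degree of disability as the single primary form, state its WHODAS 2.0 threshold, and make the total score supportive.
- Move the mental, physical and cognitive trajectories to the secondary objectives, and take 6-month disability out of them.
- Add one primary analysis to the Quantitative analysis section with that outcome, form, time point and contrast.

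No new data or patients are needed for the first route. The trajectory results become secondary. The study began in October 2020 and each site's ethics committee approved the protocol, so a dated amendment is needed, with a record that the change was made before results were seen.

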palpable contraction; 1 = visible / palpable contraction or no limb movement; 2 = limb movement, but not against gravity; 3 = movement against the gravity over nearly the entire range of motion; 4 = motion against gravity and resistance, subjectively adjusted for gender and age; 5 = normal force). This scale requires an estimated assessment time of 5 to 10 minutes and will be evaluated only at ICU discharge following the method described by Hermans *et al.*[21]

Functional Status Score for the Intensive Care Unit (FSS-ICU)

The FSS-ICU is a mobility instrument to score the level of physical assistance required when performing five functional activities: rolling, transfer from supine to sit, sitting at the edge of the bed, transfer from sitting to stand, and walking.[22] Each activity is scored using a 7-point scale ranging from 0 (not able to perform) to 7 (complete independence). The resulting overall score ranges from 0 to 35 points. Each evaluation requires between 10 and 30 minutes. It will be assessed at ICU discharge using the available and validated Chilean version.[23,24] Due to the limitations during the pandemic, walking will be evaluated inside the room, forcing the patient to walk with more laps than usual.

Montreal Cognitive Assessment–Blind (MoCA blind)

The MoCA blind is a cognitive screening tool designed to detect cognitive dysfunction in five areas: memory, attention, language, abstraction and orientation. It requires 5 minutes to be completed.[25] Each domain is scored separately for a total score ranging from 0 to 22 points. A score equal to or greater than 18 points is considered normal cognition. To minimize memory bias, the MoCA blind will be

assessed using version 7.1 at ICU discharge (in-person), version 7.2 at 3 months (by telephone) and version 7.3 at 6 months (by telephone),[26,27] following the standardised procedure recommended at <https://www.mocatest.org>.

Hospital Anxiety and Depression Scale (HADS)

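### MoCA-blind versions 7.1, 7.2 and 7.3 are given in one fixed order, so version cannot be separated from visit in the within-cohort cognitive time course; the COVID-19 versus other-causes contrast is largely unaffected

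*Combined protocol and SAP*

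**What the plan says.** In the Combined protocol and SAP, under Secondary outcomes measures, the MoCA-blind subsection gives the reason for changing version ("To minimize memory bias, the MoCA blind will be") and then the schedule: version 7.1 in person at ICU discharge, then "version 7.2 at 3 months (by telephone) and version 7.3 at 6 months (by telephone". There is one sequence for all patients. On scoring it says "Each domain is scored separately for a total score ranging from 0 to 22 points", and it applies one threshold at all visits: "A score equal to or greater than 18 points is considered normal cognition".

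The primary objective, at the end of the Introduction, is to "compare the trajectory of mental, physical and cognitive impairments at ICU discharge, 3 and 6 months" in ventilated adults "who survived an ICU stay due to severe COVID-19 or other causes, during the pandemic". In Table 2 the MoCA-blind is the only instrument under cognitive functioning, and it is given at all three visits.

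Under Quantitative analysis, "The trajectory for each outcome measure will be estimated using longitudinal multilevel regression". No term for test version or mode of administration is mentioned. The documents describe no rotation of versions, no equating, and no evidence that the three versions are equally hard. Two Spanish-language MoCA references are cited at the version schedule, but nothing is reported from them on equivalence.

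**The concern.** Changing the version between visits is a sensible guard against patients remembering items. The difficulty is the single order. If 7.3 is slightly harder than 7.2, the cohort appears to decline between 3 and 6 months; if it is slightly easier, the cohort appears to recover. Because nobody takes 7.2 at 6 months or 7.3 at 3 months, no later analysis can tell these apart.

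Two results are exposed: the time course of the MoCA score within the cohort, and the share below 18 at each visit. The scale has only 22 points and one cut-off serves all versions, so a small shift could matter if scores cluster near 18.

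**Working it through.** The plan states no figure to reproduce here. The check has four parts.

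**1. Can version be separated from visit?** Take a design with an intercept, two visit indicators (3 and 6 months) and two version indicators (7.2 and 7.3), five columns in all.
- Fixed order, as planned: the 7.2 column equals the 3-month column, and the 7.3 column equals the 6-month column. Rank is 3 of 5. Adding a column for telephone mode leaves it at 3 of 6.
- Three rotated sequences (7.1-7.2-7.3, 7.2-7.3-7.1, 7.3-7.1-7.2): rank is 5 of 5, so version can be estimated. With the mode column added it is 5 of 6, so mode stays tied to discharge versus later visits.
- Only 7.2 and 7.3 alternated, with 7.1 always at discharge: the two version columns sum to the two visit columns, which is one dependency, so rank is 4 of 5. The 7.3-versus-7.2 difference can be estimated; 7.1 stays tied to discharge.

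For the 3-to-6-month change, write d for the true change and v for the difficulty offset of 7.3 relative to 7.2. The order 7.2 then 7.3 observes d + v, and the order 7.3 then 7.2 observes d − v. The mean of the two is d and half their difference is v. The planned order observes only d + v.

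**2. Where does a shift go?** Put a pure version shift of 0.5 on 7.2 and 1.0 on 7.3, with no true change, into a linear model with visit, group and group-by-visit terms. Under the fixed order the visit coefficients are 0.5 and 1.0, and the group-by-visit coefficients are 0 and 0. With the three rotated sequences in equal numbers the visit coefficients are 0.

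**3. How far could the share below 18 move?** The documents give no SD, mean or version difference, so these are assumptions: SD 3, mean 18 or 19, one version 0.5 or 1 point harder. The share is Φ((17.5 − mean)/SD).

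| Shift | Mean 18 | Mean 19 | Difference |
|---|---|---|---|
| none | Φ(−0.167) = 43.4% | Φ(−0.500) = 30.9% | 12.5 points |
| 0.5 harder | Φ(0) = 50.0% | Φ(−0.333) = 36.9% | 13.1 points |
| 1 harder | Φ(0.167) = 56.6% | Φ(−0.167) = 43.4% | 13.2 points |

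Within a group the share moves by about 6 to 13 points. If the two means are read as two groups, the contrast between them moves by only 0.6 to 0.7 points.

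**4. Could version alone produce a significant 3-to-6-month change?** Use n = 289 (Sample size calculation, 6 months), two-sided alpha 0.05, and assumed SD 3 to 4 with within-patient correlation r of 0.5 to 0.7. The standard error of the mean change is SD × √(2(1 − r))/√n. For SD 3 and r = 0.5 this is 3/17 = 0.176. A 0.5-point shift is then 2.83 standard errors and is significant 81% of the time. Over the assumed range:
- 0.25-point shift: 19% to 45%
- 0.5-point shift: 57% to 96%
- 1-point shift: 99% to 100%

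**The case against.** The strongest reply is that the primary objective compares groups, and the groups share a version at every visit. This stands. A common additive shift cancels exactly in the group-by-visit terms, and the between-group prevalence contrast barely moves. A reader might infer that the fixed order biases the COVID-19 comparison; the documents do not support that. A ceiling at 22, or a version effect that differs by group, could still reach the contrast, but nothing in the text points to either.

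Four further replies carry weight.
- Nothing shows that the versions differ in difficulty. The cited references may address it, but the text does not say. The figures above are conditional, and means of 18 to 19 lie where the share below 18 is most sensitive.
- Quantitative analysis names HADS, IES-R and WHODAS 2.0 as analysed by category, and the MoCA-blind is not among them. The share below 18 is a likely descriptive result, since a cut-off is given and the Introduction's hypothesis refers to prevalence. It is not an explicitly planned model outcome.
- The MoCA-blind is a secondary outcome. The primary outcome, WHODAS 2.0 at 6 months, has a cognition domain that does not depend on MoCA version, although it is self-report and not a cognitive test.
- Between discharge and 3 months the mode and the assessor also change, from physiotherapists in person to interviewers by telephone. Rotating versions does not remove this.

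These replies limit the weight of the point. They do not answer the aliasing itself. From 3 to 6 months version is the only planned change in the test, and there the remedy works.

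**Conclusion.** The aliasing of version with visit is certain and follows from the schedule alone. Any version difference enters, one for one, the within-cohort MoCA time course and shifts the share below 18 at each visit. Whether there is a difference, and how large, cannot be determined from the documents. The 6 to 13 percentage points, and the 57% to 96% chance of a spurious 3-to-6-month change from a 0.5-point shift, rest wholly on the assumed SD, means, correlation and shift. They show sensitivity, not a demonstrated bias.

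A reader might go further and conclude that all of the cognitive part of the primary objective is compromised. That does not follow, because the between-group comparison at its centre is largely unaffected. The point is a cheap improvement to one secondary outcome's time course.

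**What to change.** - For patients not yet assessed at 3 months, alternate 7.2 and 7.3 between the two telephone visits, by study number within site.
- For patients not yet enrolled, rotate all three versions if sites can do so without retraining. Fifty-eight physiotherapists have already been trained for the discharge assessment, so this part is optional.
- Record the version used at each assessment and add version as a fixed effect in the MoCA trajectory model. Patients already tested in the fixed order leave the two orders unequal, so the simple average over patients would not remove the version effect; the term is needed.
- State that the change from ICU discharge to 3 months is confounded with mode and assessor, and interpret it only as a between-group contrast.

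Each patient still sees three different versions, so the guard against recall is kept. The cost is a sequence list, one recorded field and one model term, with no added visit or patient. The downsides are handling more than one version per visit and slightly more within-patient noise, mostly absorbed by the version term.

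Recruitment runs from October 2020 to April 2021, so the last 3-month calls fall around July 2021. If that window has closed, report any evidence that the Spanish versions are equivalent, or limit MoCA inference to between-group contrasts at each visit and state the limitation.

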the rest areas to capture a wider population. We will recruit medics, nurses, healthcare assistants and physiotherapists that normally work in an ICU and have patient-facing clinical duties for more than 96 hours during the pandemic. The invitation to participate will lead to a google form containing information about the study and a short script that constitutes the informed consent. From the list of volunteers, we will purposely sample three professionals per clinical group aiming to maximise variation regarding years of experience and centre where they work. We expect a minimum of 40 interviews, but we will continue recruitment until data saturation is achieved. Interviews will be conducted online or over the phone. Participants will be asked for verbal consent before starting the interview, which will be recorded for later transcription verbatim. Interviews will be semi-structured covering five main topic areas: preparation before the pandemic; intellectual, physical and emotional challenges during the pandemic; and learning for future events.

Follow-up feasibility

The consent rate will be collected, calculating the number of patients who agreed to participate divided by the number of patients who meet selection criteria, expecting a consent rate of > 70%. [39] The feasibility over-time during the follow-up will be measured as cohort retention rate, considering the number of patients who can be contacted and evaluated at 3 and 6 months. [40,41] The reasons for the lack of assessments will be recorded individually.

Sample size calculation

All patients meeting the eligibility criteria discharged from ICU between October 2020 and April 2021 (due to funding constraints) will be invited to participate.

Based on bed capacity and patient flow from previous years, we estimated that 20 to 30 mechanically ventilated adult patients are discharged monthly from each centre. This means the sampling universe ranges from 840 to 1260 patients.

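### Administrative challenges (staff objective) and organisational structure (staff hypothesis) are not among the five main staff interview topics, so neither is assured in every interview

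*Combined protocol and SAP*

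**What the plan says.** The relevant statements are in three parts of the document.

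- **Introduction, secondary objectives.** The staff objective is "To explore the emotional, intellectual, physical and administrative challenges faced by the participating ICU staff during the COVID-19 pandemic".
- **Introduction, hypotheses.** For staff, experience is expected to differ by profession and workplace, and "we expect places with a more open/ less hierarchical structure to have coped better with the increase in demand".
- **Critical care staff interviews.** The section says: "Interviews will be semi-structured covering five main topic areas". The five are preparation beforehand, "intellectual, physical and emotional challenges during the pandemic" (three topics), and lessons for later events. Participants are sampled purposively, "aiming to maximise variation regarding years of experience and centre where they work".

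The Qualitative analysis section then sets the aim for the staff data: to examine how far each centre's way of handling the pandemic shaped the experience of the clinical groups. The initial coding framework is to be formed from common topics that two coders identify after going through all the interviews.

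**The concern.** The objective and the topic list are parallel lists of challenge types, and one entry in the first is missing from the second. The staff hypothesis also turns on a feature of the centre, its openness or hierarchy, that no listed topic names.

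If the interviews follow the listed topics, material on administration and on how each centre was run depends on whether the interviewee or the interviewer brings it up. That could differ by profession and by centre. The framework is built from what was discussed, so a subject raised in only some interviews may enter it thinly or not at all. Silence from a centre would then be ambiguous: it could mean that there was no administrative difficulty, or that nobody was asked.

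**Working it through.** No sample-size or power calculation applies. The check is a count and a comparison of the lists.

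**1. Reproduce the stated number of topics.** Critical care staff interviews gives five. Counting the items: preparation (1) + intellectual, physical and emotional challenges (3) + learning (1) = 5. The count agrees, so the list is complete and no administrative item has dropped out in reading the file.

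**2. Compare the objective with the topic list.**

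| Challenge type in the objective | Own main topic? |
|---|---|
| Emotional | Yes |
| Intellectual | Yes |
| Physical | Yes |
| Administrative | No |

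Carried over: 3 of 4. Missing: 4 − 3 = 1.

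**3. Compare the hypothesis with the topic list.** Topics that name structure, hierarchy, management or decision-making: 0 of 5.

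**4. Look for another source of the same information.** Study design and setting describes the centres as academic, as four public and three private hospitals, and by pooled ICU bed capacity. Centre is also a sampling dimension for the staff interviews. Neither records how open or hierarchical a centre is, and no other section provides for collecting it.

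**5. Ask whether the remaining two topics fill the gap.** Preparation concerns the time before the pandemic, whereas the objective concerns challenges during it. Learning is retrospective and could draw in organisational matters, but it does not ask for them by name. The plan gives each of the other three challenge types a topic of its own and so does not leave those to chance.

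**6. Gauge how thin the material per centre could be.** The plan expects at least 40 staff interviews, and there are seven centres. If they were spread evenly, which is an assumption, 40 / 7 ≈ 5.7, or about six per centre, shared among four professional groups. With so few, a subject raised by only some interviewees gives little basis for describing a centre.

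**The case against.** The strongest reply is that the document does not contain the interview guide. It gives a one-sentence summary of main topics for semi-structured interviews, and the questions and probes are not shown. Organisational matters could come up under preparation or under learning, which looks back over the whole period. The stated analysis aim shows that the centre's approach is an intended line of inquiry, and a framework built from the interviews can code themes that were not listed in advance. All of this stands. It limits the consequence to coverage that is not assured. It does not remove the mismatch, because an analysis aim does not guarantee that a question is asked.

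Three stronger readings are tempting, and the document does not support them.

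- A reader might infer that administration is absent from the topic guide. Only its absence from the listed main topics can be shown.
- A reader might infer that centres cannot be compared. Centre is a sampling dimension, and themes are meant to capture similarities and differences across subgroups, so centres can be compared on staff experience. What is less secure is consistent material on administration and structure.
- A reader might infer that the missing challenge type is the only one tied to the staff hypothesis. The hypothesis is about coping, which bears directly on the three challenge types that are listed. Administrative challenges and hierarchy are also not the same thing: the first are burdens on staff, the second is an attribute of the centre. A question on administrative burden alone would not show how open a centre is.

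**Conclusion.** The mismatch is real and can be verified in the text. One of four challenge types in the staff objective, and the centre characteristic named in the staff hypothesis, are not among the five main interview topics. As written, neither is assured to be asked of every interviewee, so comparing centres on administration and structure would rest on uneven material.

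This assumes that the unseen guide follows the listed topics and has no standard question on these matters. If it already has one, the point reduces to a wording correction in the protocol.

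The point is minor. It concerns one secondary, exploratory, qualitative objective and has no bearing on the primary outcome, the sample size or the quantitative analysis. It is worth acting on because the remedy is cheap and helps the study answer its own question.

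**What to change.** Before staff interviews begin, add a sixth main topic, asked in every staff interview: administrative and organisational challenges during the pandemic, including how decisions were made in the centre. The part on decision-making is needed for the hypothesis as well as the objective. The list would then hold 5 + 1 = 6 topics and cover 4 of 4 challenge types.

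If the working guide already asks this of everyone, say so in Critical care staff interviews. If it will not be asked, remove the administrative element from the objective and narrow the hypothesis to match.

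The cost is one line in the guide, a few more minutes per interview and possibly an ethics notification. Staff recruitment is planned to start only when ICU occupancy is back to normal, so a change made before then loses no data.
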